## 4 Exclusion Criteria.

No minors (under the age of 18) will be enrolled in this study as participants or subjects. For subjects, obese and underweight humans will be excluded. Note that at the pre-submission supplement meeting, FDA agreed with a precaution statement for obese patients.

Exclusion criteria for the pre-hospital (novice) participants are as follows:

- Current or former instructor of cricothyrotomy, airway management, or anatomy
- Experience performing cricothyrotomy on a patient in the last 6 months
- Training on cricothyrotomy in the last 3 months
- Previous or current participation in a study related to cricothyrotomy
- Any condition or physical impairment that limits dexterity and/or tactile feedback
- Performed two or more cricothyrotomies on live humans
- Previous exposure to the SureCRIC

Exclusion criteria for the subjects are as follows:

- Previous exposure to the SureCRIC
- Age under 18 or over 60
- Any skin condition including, but not limited to, eczema and hives
- Skin that is thin, fragile, sensitive and/or prone to redness or irritation including skin that maintains a red, irritated appearance after the light application of pressure
- Easy bruising or use of any blood thinning medication (including aspirin)
- Beard on the neck
- Use of a steroid medication by mouth or in a topical formulation like a cream or ointment
- Any of the following chronic conditions: chronic kidney disease, chronic liver disease, coagulation disorders such as hemophilia or von Willebrand disease, low or dysfunctional platelets (e.g., thrombocytopenia), leukemia, Cushing's syndrome, Ehlers Danlos syndrome, celiac disease, any condition that causes easy bruising or sensitive or fragile skin.
- Previous neck surgery, previous neck trauma, thyroid mass or enlargement, or other neck abnormalities
- Any condition that would make lying supine or without a pillow painful or impossible

Exclusion criteria for the experienced users are as follows:

• Previous exposure to the SureCRIC

# 5 Vulnerable Subjects.

Though not specifically planned or expected, it is possible that hospital / health system employees will be included as participants. No hospital or health system employees will be included as subjects. Participants and subjects will be protected in two ways. First, no identifying information will be recorded during the study, except for faces of the participants, subjects, and study investigators. Third-party recruiters and administrative staff will coordinate logistics of participants and subjects; therefore, researchers do not need or have access to participants' and subjects' phone numbers or emails. Once participants and subjects have signed their respective consent forms, there will be no connecting information between the person and their participant number or subject number. The data that is collected and analyzed will not contain any identifiers regarding subject name, date of birth or any other identifiers. Secondly, the recruitment material and information letter will make it explicitly clear that participants and subjects are free to end participation at any point in the study.

#### III. METHODS AND PROCEDURES

## 1 Methods and Data Analysis (Human Study)

The study will be a two-arm, open-label study. The Control Group will perform CTM identification with the standard, freehand approach. The Experimental Group will perform CTM identification with the help of the SureCRIC. The Experimental Group will be trained on

SureCRIC operation prior to testing. The expert verifier will not be blinded in order to reduce any error that may be introduced by SureCRIC removal and subsequent skin movement. Participants in the human study will complete study sessions that will consist of the following:

- 1. Signing of Documents and Pre-Evaluation Interview (~5 minutes). Prior to study participation, relevant information on clinical experience will be collected from all participants. Sample data points include handedness, years of and nature of clinical experience, cricothyrotomy training, and previous cricothyrotomy performance. Upon arrival, participants and subjects will be asked to sign an informed consent form that describes their role in the evaluation, explains risks involved, and consents to the use of audio and video recordings for analysis purposes. Participants and subjects will also be asked not to disclose any information about the product or materials they see during the training and evaluation.
- 2. Device Training (approximately 30 minutes Experimental Group only). Participants assigned to the Experimental Group will undergo SureCRIC training by [name]. SureCRIC training will consist of a review of the Instructions for Use (IFU) and supervised practice on a manikin and the trainer following a brief introduction to the device and operation. A copy of the IFU is attached. Participants assigned to the Control Group will not undergo SureCRIC training. Audio and video recording will be utilized for reference and use in data reduction and analysis (if applicable). Cameras will be positioned on tripods so as not to interfere with the training.

After completion of the training, the Human Factors Center will individually interview each participant using open-ended questions to garner subjective feedback on the training and instructional materials, as well as preparedness to perform SureCRIC-aided procedures.

- 3. Decay Period (minimum 60 minutes Experimental Group only). After training, Experimental group participants will be removed from the facility for a minimum of 60 minutes. Participants will then report to the testing facility at an agreed-upon time.
- 4. Testing (approximately 30 minutes). Prior to the participants returning to the test facility, the expert confirmer may, at his/her discretion, palpate the neck surface anatomical landmarks of the subjects to familiarize himself/herself with the anatomy. An ultrasound machine will be available to help the expert confirm anatomical landmarks if desired. Subjects may also have neck measurements taken (e.g., neck circumference and length). The verifier may also place a popsicle stick on the neck to indicate the position of the cricothyroid membrane. Pictures of the neck may be taken.

  After returning to the testing facility, Experimental Group participants will utilize the SureCRIC to perform various scenarios. Control Group participants will utilize a freehand approach to perform various scenarios. Subjects will be positioned supine with their necks in the neutral position consistent with standard practice for trauma patients. Testing is the only portion of the study where subjects will be involved.

During each scenario, participants will identify the CTM on one of the six subjects. Control Group participants will perform CTM identification freehand and Experimental Group participants will use the SureCRIC as an aid in CTM identification. Participants will be made aware that they will be timed prior to testing.

Once the participant has identified the CTM, he/she will gently place a popsicle stick with smooth, round edge on the CTM. The expert verifier will then take control of the stick. The SureCRIC, if used, will then be carefully disassembled with the stick in place. Pictures of the stick on the skin may be taken with the popsicle stick on the neck. The expert verifier will palpate the structures of the anterior neck to confirm accurate CTM localization. In the Experimental Group, the SureCRIC device may be gently and intentionally shifted in position by the verifier as he/she palpates the neck. The expert verifier will indicate to the NCHFH staff (but not the participant) whether the popsicle stick is at the level of the CTM and at the midline of the neck.

After each CTM identification, the participant will report their confidence in accurately identifying the CTM. A slight modification to the procedure described by Lamb [2015] may be used, employing a 10-cm horizontal visual analogue scale (VAS) ranging from "very confident" (0) to "not at all confident" (10).

Only one subject will be available for CTM identification at a time though ultimately each participant will palpate each subject's neck, serially. The medic will not be informed of the success or failure of their identification attempt until the end of their involvement in the study. CTM identification attempts may be recorded for off-line analysis as needed.

Scenarios will include the following:

- Scenario #1: CTM identification of Subject 1 (with or without SureCRIC)
- Scenario #2: CTM identification of Subject 2 (with or without SureCRIC)
- Scenario #3: CTM identification of Subject 3 (with or without SureCRIC)
- Scenario #4: CTM identification of Subject 4 (with or without SureCRIC)
- Scenario #5: CTM identification of Subject 5 (with or without SureCRIC)
- Scenario #6: CTM identification of Subject 6 (with or without SureCRIC)

Each session will be observed by at least one Human Factors Center moderator, who will only be present to observe and give instructions and will not help participants with task completion in any way. Audio and video recording will be utilized for post-hoc data analysis. NCHFH staff will observe each CTM identification procedure focusing on procedural performance and usability in both user groups. NCHFH staff will additionally observe performance of critical tasks and essential tasks.

- 5. Semi-structured Interviews and Critical Error Debriefing (~15 minutes). Human Factors Center moderators will follow up with participants on any critical errors, close calls, or confusion/difficulty observed during task completion to determine the participant's perspective on the root cause of the error(s). Feedback will also be collected regarding perceived difficulty and usability of the device and IFU for the Experimental Group. Also for the Experimental Group, time is allotted for the moderator to ask the participants open-ended questions regarding their overall impressions of the SureCRIC, whether any tasks were particularly difficult to perform, whether training was adequate and how it might be improved, use of instructions during testing, and thoughts about SureCRIC use in the field.
- 6. Labeling Validation (~15 minutes Experimental Group only). After completing use scenarios, the session moderator will complete a labeling validation study by having Experimental Group participants to review the IFU and/or device labeling and asking

content-related knowledge questions. Per FDA's request, results of the labeling validation portion of the study will be compared to existing data from the formative SureCRIC evaluation.

Human Study Data Analysis. Through direct observation as well as video/audio data reduction and analysis, usability test measures will be taken to evaluate the safe and correct performance of critical tasks and other essential tasks. Both performance data and participant feedback will be collected. Given the limited sample size and non-numerical nature of much of the data (e.g., subjective feedback), raw data presentation will be made. In compliance with FDA request, the study will present descriptive data only, as it is not designed for statistical analysis. Also, as discussed in the pre-submission meeting, no comparisons will be performed. A description and analysis of all usability issues will be presented along with root causes and implications for additional risk elimination or reduction.

Descriptive data only will be presented for each subject -A, B C, D, E, and F. The study is not designed for statistical comparisons between the Control (i.e., freehand) and Experimental (i.e., SureCRIC) groups. The following is an example of a summary data table that will be presented. Note that the data points presented in this table are placeholders used for demonstration purposely only and are not real data. As in previous studies [Bair 2015; Elliott 2010; Kristensen 2015; Lamb 2015], the "time to CTM identification" for each attempt will start when the participant first touches the subject's neck and end when the participant indicates that he/she has identified the CTM.

Example of Summary Data Table for Subject A (sample, not real, data)

Participant	Group	Success	VAS	Time to
			Visual Analog	CTM ID
			Scale	(sec)
1	Control	Υ	3	20
2	Control	Υ	9	17
3	Control	N	2	23
4	Control	N	8	19
5	Control	Υ	7	30
6	Control	N	5	35
7	Control	Υ	6	17
8	Control	Υ	4	18
9	Control	N	3	28
10	Control	N	8	23
Control Total / Average		5/10 (50%)	5.5	23
		success		
Participant	Group	Success	VAS	Time to
				CTM ID
				(sec)
11	Experimental	Υ	2	25
12	Experimental	Υ	3	19
13	Experimental	Υ	0	38
14	Experimental	N	4	22
15	Experimental	N	5	40
16	Experimental	Υ	7	15

17	Experimental	Υ	3	28
18	Experimental	Υ	6	33
19	Experimental	Υ	3	26
20	Experimental	Υ	6	30
Experimental Total / Average		8/10 (80%)	4	27.6
		success		

Human factors data will be presented in both tabular and paragraph form. These will include data on critical and non-critical tasks, subjective feedback, and labeling comprehension information. A description and analysis of all use errors and difficulties that could cause harm will be provided along with root causes of the problems and implications for additional risk elimination or reduction.

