## **Payment for Participation.**

Control Group participants in the human study will be compensated \$125 for participation of approximately 1 hour. Experimental Group participants in the human study will be compensated \$175 for participation of approximately 2.5 hours. Subjects in the human study will be compensated approximately \$30/hour, and will be present on 4 consecutive, 9-hour days, and therefore be compensated \$1,080 each. One back-up subject will be recruited for each size and compensated \$75 per day of being "on call." In the manikin study, novice participants will be compensated \$225 for participation, and expert participants will be compensated \$750. The expert, verifier clinician will be compensated at a rate of \$250/hr. For 4 consecutive, 9-hour days, the expert verifier will be compensated a total of \$9,000.

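### Does giving same-day training to the SureCRIC arm alone spoil the freehand Control as a reference?

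*Combined protocol and SAP*

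**What the plan says.** All references are to the combined protocol and SAP.

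- **Training (III.1, item 2).** Experimental participants have a session of about 30 minutes. They review the instructions for use and have "supervised practice on a manikin and the trainer following a brief introduction to the device and operation". For the other arm, "Participants assigned to the Control Group will not undergo SureCRIC training", and no freehand refresher is described in its place.
- **Break (III.1, item 3).** After training, "Experimental group participants will be removed from the facility for a minimum of 60 minutes". The step is called a decay period and applies to that arm alone.
- **Eligibility (II.4).** Novices in both arms are excluded for "Training on cricothyrotomy in the last 3 months".
- **Session length (Payment for Participation).** Experimental medics are paid $175 for "participation of approximately 2.5 hours" and Control medics $125 for "participation of approximately 1 hour".
- **Objectives (I.2).** The first is to measure how effective SureCRIC is as an aid to finding landmarks. Another is to evaluate the user training and the instructional materials.
- **Analysis (III.1, Human Study Data Analysis).** Results are descriptive and shown subject by subject. The text says that the arms will not be compared and that the study was not designed for statistical comparison of them. The example table shows both arms' success counts, confidence scores and times.

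**The concern.** A randomised Control arm is normally there to isolate the device. Here the assigned arm carries two things, the device and supervised practice on the day, and only one arm gets either. The protocol itself seems to treat recent training as relevant: it bars medics trained on cricothyrotomy in the previous 3 months, and it names the pause after training a decay period. Controls are thus tested at least 3 months after any such training, and Experimental medics perhaps an hour after a practice session.

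If practice alone improves landmark finding, the SureCRIC success rate on the primary endpoint would exceed the freehand rate even with a device that adds nothing. Readers will look across the two halves of the table whether or not a test is planned, and the first objective invites them to credit any gap to the device.

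**Working it through.** **1. Do the stated session lengths confirm the asymmetry?** Step times are from section III.1, items 1 to 6.

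- Experimental: 5 + 30 (training) + 60 (break) + 30 (testing) + 15 (interview) + 15 (labeling) = 155 min = 2.58 h. The protocol states about 2.5 h.
- Control: 5 + 30 (testing) + 15 (interview) = 50 min = 0.83 h. The protocol states about 1 h.

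Both figures are reproduced. The Control hour contains no practice step. The Experimental total fits only if the break stays near its 60-minute minimum, since without any break it would be 95 min. So practice precedes testing by about an hour.

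**2. How large could a practice effect look?** The documents give no figure, so everything here is assumed.

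- Attempts per arm: 12 medics × 6 subjects = 72. If practice adds 5 to 20 points, 72 × 0.05 = 3.6 and 72 × 0.20 = 14.4 successes.
- For one subject, take 12 medics per arm, Control success of 50%, no device effect, and independent binomial counts X (Experimental) and Y (Control). A gap of at least 30 points needs X − Y ≥ 4, because 0.30 × 12 = 3.6.

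| Assumed practice effect | P(X > Y) | P(X − Y ≥ 4) |
|---|---|---|
| 0 points | 0.419 | 0.076 |
| 10 points | 0.616 | 0.172 |
| 20 points | 0.792 | 0.324 |
| 30 points | 0.918 | 0.525 |

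A practice effect of 10 to 20 points would make a visible gap more likely. The first row shows that chance alone gives the SureCRIC arm the higher count on a subject about 42% of the time. That is a reason not to read these tables as comparisons at all, which is the protocol's own position.

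**3. What in the plan would be biased?** There is no alpha, power, margin, effect estimate or pass threshold for the difference between arms. Each arm's rate is reported for what it is: success by trained SureCRIC users, and success by medics working freehand as they arrive. A practice effect distorts neither rate as a description of that arm.

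**4. What would training the Controls do?**

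- Cost: 12 × ($175 − $125) = $600 in payments, and 12 × 0.5 h = 6 h of trainer time if sessions are individual. Sessions would run 5 + 30 + 60 + 30 + 15 = 140 min, about 2.3 h, because Controls have no labeling step.
- Effect on the question: Control would no longer show how medics perform without a refresher.
- Effect on balance: 30 minutes spent wholly on freehand landmarks is more such practice than the Experimental arm gets, since its 30 minutes also cover the instructions for use and device handling. The imbalance could reverse.

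**The case for a change.** The best case for a change is that a reference arm will be used as a reference whatever the analysis text says, and that a study with no formal analysis has only its labels to guard against misreading. The example table calls the arms simply Control and Experimental. Naming them as SureCRIC with same-day training and freehand without training would cost nothing.

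Part of this stands. A gap between the arms cannot be credited to the device alone, and a careful report would say so. But section I.1 and section III.1 already state that training and the break belong to the SureCRIC arm only. A new label would repeat a disclosed fact and alter no result.

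Other parts are weaker than they look:

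- **Content of the training.** The protocol describes training in operating the device, with practice on a manikin and on the trainer. Rehearsal of landmark finding on a live neck is a plausible reading, given the device's purpose, but it is not stated. The instructions for use are not among the documents available here.
- **The 3-month exclusion.** Section II.1 explains the selection as keeping out medics with unusual cricothyrotomy knowledge, so that the sample is the hardest user group. It applies to both arms and does not show that a half-hour device session improves landmark finding.
- **The break.** It does not equalise the arms, but it is a deliberate limit on immediate carry-over from training.

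One argument for the plan should not be pressed. The protocol says that its design and methods follow regulator feedback, but it does not show that this particular asymmetry was discussed.

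**Conclusion.** No change follows. The asymmetry is real and confirmed by the session times. It makes the observed contrast one of device plus same-day training against unrefreshed freehand practice. That is a fair contrast for a validation study that also sets out to evaluate the training, and medics with no previous exposure to SureCRIC could hardly represent trained users without it. Matched training for Controls is a trade-off between two questions and corrects no error.

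The effect on planned inference is nil, because none is planned between the arms. The effect on an informal reading is unknown: the 3.6 to 14.4 successes out of 72 and the table probabilities rest wholly on assumed practice effects and an assumed 50% Control rate. The conclusion depends on the report keeping to the protocol's commitment to descriptive results without comparison. Analysts who do so can be expected to describe the SureCRIC results as those of trained users.

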## 2 Purpose of the Study

Overall validation study objectives are:

- To measure SureCRIC effectiveness with regard to the intended use of helping to identify anatomical landmarks
- To demonstrate that SureCRIC can be used by representative users under simulated conditions with minimal critical errors
- To evaluate the effectiveness of user training and instructional materials

The human validation study is one of two parts of the final evaluation method intended to demonstrate the safety and effectiveness of the device, labeling and related materials (e.g., materials, packaging, labeling). From the human factors perspective, the validation study serves to ensure that risks associated with the use of a medical device have been identified and adequately addressed, and that the impacts of residual risks are minimized. InnoVital Systems, Inc. (InnoVital) has engaged the National Center for Human Factors in Healthcare (Human Factors Center) to conduct the validation (also referred to as summative) study for the SureCRIC. Validation conducted by the Human Factors Center will focus on evaluating the use of the device by its intended users in simulated use environments. Specifically, the objectives of the human evaluation are:

- Primary endpoint: pass/fail assessment for CTM identification. The use of ultrasound to predefine / pre-mark CTM boundaries on the skin was discussed in the pre-submission supplement meetings. However, internal testing suggests that skin movements with SureCRIC use, and small head and neck movements by subjects may cause the pre-marked skin to shift and result in inaccurate assessments. This finding is in line with the limitations reported in a recent study evaluating CTM identification success in conscious human volunteers [Lamb 2015]. For the purposes of the current study, and as discussed with FDA, an expert in neck / airway anatomy (e.g., otolaryngologist or trauma surgeon) will palpate the area to verify accurate CTM localization.
- Secondary endpoints: time to CTM identification will be measured for descriptive statistics only per FDA request. Additionally, medics will be asked to report their confidence in accurate CTM identification (e.g., on a visual analog scale). Preparticipation, post-training, and post-participation human factors data will also be collected, as well as data from labeling validation.

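### Does the plan leave open whether the SureCRIC is still on the neck when the expert gives the primary pass/fail verdict?

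*Combined protocol and SAP*

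**What the plan says.** Section I.2 (Purpose of the Study) makes pass/fail identification of the cricothyroid membrane (CTM) the primary endpoint of the human study. It explains why ultrasound marks on the skin were dropped: "skin movements with SureCRIC use, and small head and neck movements by subjects may cause the pre-marked skin to shift". In their place, an expert in neck and airway anatomy "will palpate the area to verify accurate CTM localization", an approach the section says was discussed with FDA.

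Section III.1 gives the reason for an unblinded verifier: "The expert verifier will not be blinded in order to reduce any error that may be introduced by SureCRIC removal and subsequent skin movement". Item 4 (Testing) then sets out the steps after the participant has placed the stick:

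1. "The expert verifier will then take control of the stick".
2. "The SureCRIC, if used, will then be carefully disassembled with the stick in place".
3. "The expert verifier will palpate the structures of the anterior neck to confirm accurate CTM localization".
4. In the Experimental Group, "the SureCRIC device may be gently and intentionally shifted in position by the verifier as he/she palpates the neck".
5. The verifier tells the staff, but not the participant, whether the stick is at CTM level and in the midline.

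The same item permits, without requiring, a palpation of each subject before testing, use of an ultrasound machine, a reference stick placed by the verifier, and photographs.

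**The concern.** Steps 2 and 4 seem to conflict. If the device has come apart and is off the neck before palpation, there is nothing left to shift. If part of it is still there, the text does not say which part. Nor does it say who takes the device apart while the verifier holds the stick, and the moderators "will not help participants with task completion in any way".

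This step produces the primary endpoint, and the ambiguity touches one group only. If some SureCRIC verdicts were given with a component on the neck and others without, the success counts tabulated for each subject would mix two measurements. Deliberate shifting could also move the skin under the stick, in a plan that itself names skin movement as a source of inaccurate assessment.

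A second worry follows. One verifier judges each neck many times over four days, and no record of that neck's CTM level has to be made beforehand. A level misjudged once could be misjudged throughout.

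**Working it through.** The plan states no sample size calculation, alpha or power for this endpoint, so there is no design figure to reproduce. The check is a count of the verdicts involved and a comparison of the sentences.

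**Counts.** Inputs: 24 participants, half in each group, and 6 subjects (section I.1); every participant examines every subject (section III.1, item 4); 4 days of 9 hours (Payment for Participation).

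- All verdicts: 24 × 6 = 144, or 144 / 4 = 36 a day.
- SureCRIC verdicts: 12 × 6 = 72. Control verdicts: also 72.
- Verdicts per neck: 24, or 24 / 4 = 6 a day, in line with the 5 to 6 sessions a day in section IV.2.
- If one neck were misjudged at every palpation: 24 / 144 = 16.7% of all verdicts, and 12 / 72 = 16.7% in each group.

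The 72 is the number of attempts that pass through the unclear step. It is not a number of errors. The 16.7% is a ceiling that needs the same mistake at all 24 palpations of one neck, and it falls equally on both groups.

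**Do the sentences conflict?** Two readings make them agree.

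| Reading | Disassembly sentence | Shifting sentence |
|---|---|---|
| Disassembly is partial | Some parts come away, the stick stays | The verifier may move what remains while palpating |
| Palpation begins before disassembly | The device comes apart during verification | Shifting happens in the early part of the palpation |

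The protocol states neither. The Instructions for Use, attached to the protocol but not available here, may describe how the device comes apart. On both readings the verifier has control of the stick before disassembly, and the criterion (level and midline) is the same.

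**Does the reason for not blinding conflict with the sequence?** No. A verifier who takes the stick and holds it while the device comes off must see the device. Holding it is also the protection against error from removal and skin movement, which is the purpose section III.1 gives.

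**Would verdicts be reached in mixed ways?** The text sets one sequence for every SureCRIC attempt. The word *may* makes the shifting optional for the verifier. It does not say that the device is present on some attempts and absent on others.

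**Who disassembles?** By this point the participant has identified the CTM and placed the stick, and the timed interval ends when identification is indicated (Human Study Data Analysis). The limit on moderators concerns the participant's task, so it does not clearly bar staff from taking the device apart.

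**What would a required check before testing cost?** Assume 5 to 10 minutes per neck, a figure the documents do not give. Six necks take 30 to 60 minutes, and twelve, if every back-up is used, take 60 to 120 minutes. Against 4 × 9 = 36 verifier hours that is 0.5 / 36 = 1.4% to 2 / 36 = 5.6%. Time is the smaller part of the cost. None of the verifier qualifications in section II.3 requires ultrasound skill, so the verifier would have to be chosen for it or an operator brought in. Ultrasound is also absent from the procedures listed for subjects in section IV.2, so that section would need a line and the consent text a check.

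**The case for a change.** The strongest case for a change is that this is the primary endpoint and the first remedy costs only wording. A reader cannot tell from the protocol what is on the neck when the verdict is given, and even a descriptive proportion needs one defined measurement. The plan recognises skin movement as a hazard and then permits deliberate shifting in one group only. On the reference standard, the reason for rejecting skin marks does not count against a single ultrasound check per subject, recorded against the cartilage landmarks.

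Part of this stands. The state of the device at the verdict is not stated, and one clarifying sentence would help. It is also true that the skin-mark argument does not rule out an ultrasound check that leaves no mark. The rest is weaker:

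- The warning about skin movement concerns marks drawn in advance, whereas here the verifier holds the stick and palpates the structures directly.
- No passage shows two procedures in use, and the documents do not allow any bias to be sized.
- A required check before testing would not change how a verdict is reached. Palpation after each attempt would still decide, applying the record would still depend on finding the cartilages by palpation, and no rule would say how the record could overturn a result.

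**Conclusion.** No change to the plan follows. The two sentences leave a real but minor gap, which a verifier and staff who have the device and its instructions in front of them can settle sensibly before the first attempt. The gap touches 72 of 144 verdicts in the sense that they pass through the step. No verdict is shown to be wrong or to be reached differently from the others.

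The optional status of ultrasound is a fair trade-off: expert palpation was chosen openly, with a reason, and the aids remain available to the verifier. Requiring them would call for more resources without altering the verdict.

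The consequence is limited further because Human Study Data Analysis specifies descriptive data only and no comparison between the groups, so no test, power or error rate is affected. This conclusion assumes that one sequence is followed for every SureCRIC attempt, as the Testing item describes, and that the verifier keeps hold of the stick until the verdict is given.
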